4.4.2. Investigation of general taste perception

In addition to the bitter taste, we also plan to evaluate the other four basic tastes and the metallic taste. To this end, study participants will taste mouthwash solutions containing salty (NaCl), sour (citrate), sweet (sucrose), umami (glutamate) or metallic (ferrous sulphate) flavourings and rate their taste quality. The results will be compared across visits and groups. In addition, the pilot study will also include a survey on taste perception and chemotherapy-induced taste changes using a questionnaire developed in-house. This questionnaire is based on the questions by McGettigan et al. [10] and has been supplemented with questions regarding the preference for and consumption of specific foods (attached in the appendix).

4.4.3. Assessment of food intake

The patients' food intake is recorded using a 24-hour dietary recall. A standardised questionnaire is used to determine the quantities of specific foods consumed by the patients

over the past 24 hours. The questionnaire is administered in person or by telephone using the computer-based GloboDiet questionnaire by a trained staff member.

4.4.4. Assessment of quality of life

The patients' quality of life is analysed using the EORTC-QLQ-30 and OV-28 questionnaires, whilst 'patient-related outcomes' are evaluated via a diary.

4.4.5. Assessment of Body Composition and Body Weight

We also plan to analyse the body composition and weight of the patients. For this purpose, we will use the BOD POD® device, which operates on the principle of air displacement plethysmography. Body composition, and in particular body fat percentage, is determined by calculating density based on the volume of displaced air measured within the BOD POD capsule.

4.4.6. Measurement of Chemotherapy Drug Concentration in Saliva

The pilot study aims to measure the concentration of the chemotherapy drug in patients' saliva during and after chemotherapy administration. To this end, serial saliva samples will be collected before the start of chemotherapy administration ($t=0$), during chemotherapy administration ($t=2h$), at the end of chemotherapy administration ($t=4h$), two hours after the end of chemotherapy administration ($t=6h$), and the following morning ($t=18-20h$). Before each saliva collection, the mouth is thoroughly rinsed with water. The saliva samples are stored at -80°C until processing and analysis. Before measuring the platinum concentration, the saliva matrix is digested by adding nitric acid and hydrogen peroxide and by heat treatment. The concentration of the chemotherapeutic agent is determined using inductively coupled plasma - mass spectrometry (ICP-MS), with measurements conducted by the Institute of Physiological Chemistry in collaboration with the Institute of Analytical Chemistry.

4.4.7 Measurement of Serum Zinc Concentration

In the pilot study, the concentration of the metal zinc in the patients' serum will be determined. Blood samples will be collected as part of a routine blood draw, so no additional intervention is required for the patients. The zinc measurement will be performed in the laboratory of the Medical University of Vienna as part of routine diagnostics.

4.4.7 Measurement of the concentration of the chemotherapeutic agent in blood serum

In the pilot study, the concentration of the chemotherapeutic agent in the patients' blood serum will be determined. Blood samples are collected as part of a routine blood draw, so there is no additional intervention for the patients. Measurement of drug levels will be

performed in the laboratory of the University of Vienna, Institute of Physiological Chemistry, in collaboration with the Institute of Analytical Chemistry.

4.5. Timeline

Pilot study

Recruitment	Months 1–12
Analysis	Months 12–15
Total	15 months

RCT

Study planning	Months 1–6
Recruitment	Months 7–30
Analysis	Months 30–36
Total	36 months

B) Statistical Section

1. Sample Size

Forty patients will be recruited for the pilot study. This study is intended to provide a descriptive analysis of taste changes during chemotherapy and to validate the tests used for the double-blind, randomized, placebo-controlled study planned afterwards. The double-blind, randomized, placebo-controlled study will include 32 female patients. Based on current studies [3], the prevalence of bitter phantogeusia is approximately 30–78%. An HED mouthwash leads to a 30% reduction in bitter perception (standard deviation 10%) [7], which describes the expected effect size. The primary endpoint is defined as “comparison of the bitter perception triggered by 500 ppm caffeine from week 1 to week 3 between the study group (HED mouthwash) and the control group (water mouthwash).” The patient rates bitterness perception on a continuous scale from 0 to 10. The study endpoint is therefore a continuous variable. The data from week 1 and week 3 will be analysed using a paired t-test to compare the intervention group with the control group. Taking into account a 20% dropout rate, a 90% power level, and a significance level of 1%, this results in a sample size of 32 patients. These will be randomized 1:1, resulting in a group size of 16 patients each. Approximately 77% of patients experience bitter phantosmia following platinum-based combination chemotherapy. Therefore, approximately 40 patients will need to be screened.

2. Randomization

Randomization is performed online using the randomization program of the Medical University of Vienna (<https://www.meduniwien.ac.at/randomizer/web/login.php>). The complete randomization list is provided to [name], MSc, a staff member of the Institute of Physiological Chemistry. Study medication is packaged and coded, with coding performed exclusively by [name]. The coded, randomized study medication is then distributed as needed to the investigators, who administer the study medication to the patients. The investigators and the statistician may not view the randomization list until the study has been completed.

3. Statistical Analysis

The efficacy of the treatment is defined as a reduction in the perception of bitterness by more than 30% in the treatment group compared to the placebo group. The primary endpoint will be evaluated using a paired t-test.

This will be evaluated in two analyses:

- Intention-to-treat analysis: Inclusion of all patients who used the mouthwash at least once
- Per-protocol analysis: Inclusion of patients who completed the study according to the study protocol

Secondary endpoints are also analysed using intention-to-treat and per-protocol analyses. The collected clinical and pathological data are presented descriptively using absolute values or, depending on the normality of the distribution, using the median (interquartile range) or mean (standard deviation). Metric variables are compared using Student's t-test or the Mann-Whitney U test, depending on normal distribution. Categorical variables are compared using the chi-square test and, if feasible given the number of groups, presented including the odds ratio (95% confidence interval). The study will investigate predictive factors for response to the intervention. These analyses are performed using a multivariate binary logistic regression model. The following variables are included: patient age, number of chemotherapy cycles, patient BMI, bowel resection during the primary surgery, peripheral polyneuropathy during chemotherapy, nausea at the time of study enrolment, and diarrhoea at the time of study enrolment. Version 21.0 of the statistical software SPSS (SPSS, Inc.) is used for the statistical analysis.

Patient data is pseudonymized, documented, and analysed in accordance with current data protection regulations and is not disclosed to third parties. The data is published in anonymized and aggregated form.

C) Ethical and Legal Section

1. Ethical Aspects

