3.3 Study Endpoints

Pilot Study

- Comparison of taste tests before and during chemotherapy

RCT

Primary endpoint:

- Comparison of the perception of bitterness induced by 500 ppm caffeine from week 1 to week 3 between the study group (HED mouthwash) and the control group (water mouthwash).

Secondary endpoints:

- Comparison of the perception of bitterness triggered by 500 ppm caffeine from week 1 to week 12 between the two groups.
- Comparison of the threshold for bitterness perception from week 1 to week 3 between the two groups.
- Comparison of the threshold for bitter taste perception in week 3 between the two groups.
- Comparison of overall taste perception in week 3 between the two groups.
- Comparison of overall taste perception from week 1 to week 12 between the two groups.
- Comparison of food intake using a 24-hour recall from week 1 to week 12 within the two groups.
- Comparison of food intake using a 24-hour recall from week 1 to week 12 between the two groups.
- Comparison of improvements in body composition from week 1 to week 12 between the two groups.

- Comparison of weight gain from week 1 to week 12 between the two groups.
- Comparison of quality of life using the EORTC-QLQ-30 Ovar and OV-28 from week 1 to week 12 within the two groups.
- Comparison of the change in quality of life using the EORTC-QLQ-30 Ovar and OV-28 from week 1 to week 12 between the two groups.
- Comparison of “patient-related outcomes” using a diary from week 1 to week 12 within the two groups.

4. Experimental Protocol

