1.1. The Risk-Benefit Ratio

The homoeriodictyol to be administered in this study was published on the FEMA-GRAS (“generally recognized as safe”) list 22 by the FEXPAN expert panel of the Flavor and Extracts Manufacturers Association (FEMA) in the United States and has thus been deemed generally safe. Substances published on the GRAS list do not require further approval from the Food and Drug Administration (FDA) to be authorized for the market. NaHED (FL. - Number 16.083) has also been included in the EU’s positive list of permitted flavourings (Implementing Regulation No. 872/2012, Official Journal of the European Union, L 267/1) and is provided for this study by Symrise AG, Holzminden, Germany, in the specification required for use as a flavouring.

There are no risks for study participants, and no further examinations or interviews are required. All participants who complete the study will receive compensation for their time and effort in the amount of 130.00 euros. A portion of the compensation will be paid to the participants per visit (visit 1: 50 euros, visit 2: 30 euros, visit 3: 50 euros). For participants in the HED group, a benefit in the form of a reduction in the perception of bitterness is expected. In addition, a partial reduction in the perception of bitterness may also occur in the control group due to the placebo effect. The collected data can be used to facilitate the planning of a further, larger validation study to precisely evaluate the efficacy of HED in chemotherapy-induced bitter phantogeusia.

2. Legal Aspects

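### The primary endpoint compares HED with placebo in independent patients, but the only test named for it is a paired t-test, which ignores the control if run within the HED arm or pooled over arms

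*Combined protocol and SAP*

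**What the plan says.** The contrast is between arms. Section 3.3 (Study Endpoints) gives the primary endpoint as "Comparison of the perception of bitterness induced by 500 ppm caffeine from week 1 to week 3 between the study group (HED mouthwash"), with placebo as the comparator. Part B, section 1 (Sample Size) repeats it. Part B, section 3 (Statistical Analysis) defines efficacy as "a reduction in the perception of bitterness by more than 30% in the treatment group compared to the placebo group".

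The arms are independent. Section 4.3.3 randomises patients 1:1 without strata or blocks, and no matching is described anywhere.

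The test is paired. Part B, section 1 says: "The data from week 1 and week 3 will be analysed using a paired t-test to compare the intervention group with the control group". Part B, section 3 says: "The primary endpoint will be evaluated using a paired t-test". That section also has a general rule for metric variables (Student's t-test or Mann-Whitney U), but does not attach it to the primary endpoint, which has its own instruction.

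On change without HED, part C, section 1.1 allows that "a partial reduction in the perception of bitterness may also occur in the control group due to the placebo effect".

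**The concern.** A paired t-test needs two linked measurements on each unit. In this design the natural links are a patient's own week-1 and week-3 ratings, so the test asks whether ratings changed over time, within one arm or in all patients together. That is not the randomised question.

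The setting makes the difference matter. Visit 1 takes place one week after the last chemotherapy cycle (section 4.1.1), so weeks 1 to 3 lie in the post-chemotherapy period. Patients enter because bitter perception is disturbed, and the week-1 caffeine rating is part of that assessment (section 4.3.3), so some regression to the mean is possible. A placebo response is acknowledged as possible. Each of these could lower ratings in both arms alike. A within-arm p-value cannot separate them from an effect of HED; the control arm is there to do so.

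**Working it through.** **Inputs from the documents.** 16 patients per arm; 20% dropout, so 16 × 0.8 = 12.8, about 13 evaluable per arm; significance level 1%, sidedness not stated (two-sided used below); power 90%; 30% reduction with SD 10%. The documents do not say whether that SD belongs to a single rating, a within-patient change or a difference between arms.

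**Assumed.** The change common to both arms when HED does nothing, written δ in SDs of the change score. The documents give no value, so a range is shown.

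**1. The plan's own figure.** If SD 10% is the SD of the change, d = 30/10 = 3.0.
- Two-sample t-test: 5 per arm gives 87% power and 6 per arm gives 96%. So 12 evaluable, and 12/0.8 = 15 in total.
- Paired t-test: 6 pairs, and 6/0.8 = 7.5, so 8 patients; or 15 in total if 6 are wanted in each arm.

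Neither gives 32. One-sided 1% and 5% levels give smaller totals. A total near 32 would need an SD of about 18-19% (d about 1.6 to 1.7) in a two-sample test. The stated sample size therefore does not show which test was intended.

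**2. Paired test within the HED arm, HED equal to placebo.** The rejection rate is P(|T| > t(0.995, n−1)), with T noncentral t on n−1 degrees of freedom and noncentrality δ√n. The critical value is 3.055 for n = 13 and 2.947 for n = 16.

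| δ | noncentrality, n = 13 / 16 | significant, n = 13 / 16 |
|---|---|---|
| 0 | 0 / 0 | 1% / 1% |
| 0.25 | 0.90 / 1.00 | 3.7% / 4.7% |
| 0.5 | 1.80 / 2.00 | 16% / 21% |
| 1 | 3.61 / 4.00 | 70% / 84% |

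Pooled over both arms (n = 26), the rates are 8%, 42% and 98.5% at δ = 0.25, 0.5 and 1. Testing each arm separately and comparing the p-values does not help: in simulation with 13 per arm, HED was significant and placebo was not in 13% of null trials at δ = 0.5 and 21% at δ = 1.

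**3. Two-sample test on changes.** The common change cancels (δ − δ = 0), so the noncentrality is 0 and the rate is 1% for every δ. Simulation (100,000 runs, 13 per arm, δ from 0 to 2) gave 0.97% to 1.01%.

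**4. Pairing HED patients with placebo patients arbitrarily.** The SD of a pair difference is √2 times the SD of the change, so the noncentrality d√(n/2) is the same as for the two-sample test. Degrees of freedom fall from 24 to 12, and the critical value rises from 2.797 to 3.055. With 13 pairs:
- d = 3.0 (stated inputs, SD of the change): power above 99.9% by either test.
- d = 1.65 (assumed, close to what 13 per arm can detect with 90% power): 91% for two-sample, 85% for paired.

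**5. ANCOVA against change scores.** With week 1 to week 3 correlation r and equal variances, the large-sample variance ratio is (1−r²)/(2(1−r)) = (1+r)/2. For assumed r of 0.5, 0.75 and 0.9 this is 0.75, 0.875 and 0.95.

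**6. Sample size for a between-arm test.** Step 1 gives 15 in total. If SD 10% is instead the SD at each visit, the SD of the change is 10√(2(1−r)). For assumed r from 0 to 0.75 the need is 9 to 4 per arm, or 23 to 10 in total after dropout. All are below 32.

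**The case against.** The strongest reply is that the test is only misnamed. The sentence in part B, section 1 says its purpose is to compare the groups, the efficacy criterion is relative to placebo, and section 4.4.1 says ratings are compared between groups and visits. A t-test between arms on each patient's week 3 minus week 1 change is a plausible intention. This has force: a reader might infer that the plan will credit HED with recovery or placebo response, and the documents do not support that. Nowhere do they say a within-arm result will serve as the efficacy evidence, and part C, section 1.1 says only that a placebo response may occur. What remains is that the plan names a different test, twice, and leaves the choice open.

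A reader might also infer that a paired t-test can never compare HED with placebo. That is too strong. Arbitrary pairing does test the between-arm difference at the nominal level under normality. Its faults are lost degrees of freedom and a result that depends on who is paired with whom, and the power loss is negligible on the stated inputs if the SD is that of the change.

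The false-positive rates rest on assumed shifts, and at 0.25 SD the excess over 1% is small. That stands, and is why a range is given.

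Finally, a reader might extend the fault to the secondary endpoints. Only the diary outcome is listed without a between-group comparison ("using a diary from week 1 to week 12 within the two groups"); food intake and quality of life have both kinds. That is a separate choice of endpoint, not the paired-test error.

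**Conclusion.** The point holds in conditional form. As written, the named test does not fit the primary endpoint or the efficacy criterion, and the general rule for metric variables does not override the specific instruction. If the paired test were run within the HED arm or pooled, and read as efficacy, the chance of a false claim would exceed 1% by an amount set by the unknown common change: from about 4-5% at 0.25 SD to 70-84% at 1 SD for 13 to 16 patients in one arm. If a between-arm test on changes was meant, there is no inflation and the fault is one of wording. Because the documents do not settle which, the primary analysis is not yet specified, and it should be before unblinding. The rates assume normal change scores and a two-sided 1% level.

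**What to change.** In part B, sections 1 and 3, replace the paired t-test with one between-arm primary analysis: an ANCOVA of the week-3 rating for 500 ppm caffeine on arm and week-1 rating. Report the adjusted difference with its confidence interval, and state whether the 1% level is one- or two-sided. A two-sample t-test on the week 1 to week 3 changes would also repair the mismatch; ANCOVA is preferred because in large samples it is at least as precise. Label within-arm comparisons as descriptive.

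Restate the sample-size paragraph for the chosen test, saying what the SD of 10% refers to, since 32 does not follow from the stated inputs.

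The cost is a written amendment covering these two sections and a fresh sample-size derivation. The week-1 rating is already collected at Visit 1, so there are no new measurements and, on the stated inputs, no additional patients.

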2.1. Background

Up to 77% of all female cancer patients suffer from chemotherapy-related taste disorder [1, 2]. On one hand, there is a loss of taste buds; on the other hand, tastes are perceived differently. This impairs the quality of life of oncology patients, and reduced appetite leads to decreased food intake, nutritional deficiencies, and, in the long term, increased mortality. The exact mechanism by which chemotherapeutic agents cause taste disturbances is currently not well understood [1], and no effective therapeutic interventions are available.

Cancer patients often experience a persistent bitter or metallic taste [3]. This taste disorder is called bitter phantogeusia and is associated with increased expression of the bitter receptors (TAS2Rs) 3, 42, and 43 in the taste cells of the tongue [4]. Tsutsumi et al. [5] demonstrated that patients with bitter phantogeusia who received a combination of radiation therapy and chemotherapy (cisplatin/5-fluorouracil) exhibited increased expression of TAS2R5. This effect was not observed with radiation therapy alone [5]. Furthermore, it was shown that bitter phantogeusia is more pronounced with cisplatin-containing chemotherapy, in contrast to combination therapy with cyclophosphamide, doxorubicin, or 5-fluorouracil. Nevertheless, the exact mechanism by which chemotherapy affects taste receptors is highly complex and poorly understood, which is why no effective treatments for bitter phantogeusia are currently available.

The plant-derived compound homoeriodictyol (HED) can reduce the perception of the bitter taste of caffeine by approximately 40% [7] and is currently one of the most potent bitter-masking agents. HED acts as an antagonist on the bitter receptors TAS2R20, 31, 43, and 50 [8]. In addition, it has been shown that a 30 mg bolus dose of HED has an appetite-stimulating effect in healthy subjects [9]. This amount of HED is already used by the food industry to mask bitter tastes.

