4.4. Experimental design and schedule

4.4.1. Investigation of the perception of bitter taste

In ovarian cancer patients with chemotherapy-induced bitter phantogeusia, the perception of bitterness from caffeine is tested. To this purpose, study participants are administered 20 ml of an aqueous mouthwash solution containing 500 ppm caffeine. After rinsing and spitting out the caffeine solution, the patients rate the bitterness of the solution on a scale from 0 (slightly bitter) to 10 (very bitter). The perception of bitterness is then tested in the presence of HED by administering a 500 ppm caffeine rinse solution with 100 ppm HED added. After rinsing and spitting out this caffeine-HED solution, the patients again rate the bitterness on a scale of 0 to 10. The perception of bitterness of caffeine alone and of caffeine after HED is used for comparison between groups and visits. In addition, a threshold test for bitter taste is carried out to determine the concentration of caffeine at which the patients perceive a bitter taste. To determine this, the patients taste mouthwash solutions one after the other, starting with water, at increasing concentrations of caffeine. Patients indicate the concentration at which they first detect a taste (detection threshold) and the concentration at which they can recognize a specific taste (recognition threshold), and whether the taste intensifies from one concentration to the next. The resulting threshold value for bitter perception is also used for comparison between groups and visits.

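### The stated sample-size inputs give about 16 patients, not 32, and no SD is given for the week 1 to week 3 change, so the power for the primary endpoint is unknown

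*Combined protocol and SAP*

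**What the plan says.** Section B.1 gives the effect as follows: "An HED mouthwash leads to a 30% reduction in bitter perception (standard deviation 10%) [7], which describes the expected effect size". It then states that, allowing for "a 20% dropout rate, a 90% power level, and a significance level of 1%, this results in a sample size of 32 patients", randomised 1:1 into two groups of 16. It does not say whether the test is one- or two-sided. The test named, here and in Section B.3, is a paired t-test, although the comparison is between the HED and control groups.

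Section 3.3 defines the primary endpoint as the between-group comparison of bitterness from 500 ppm caffeine from week 1 to week 3. Section 4.4.1 has each patient rate caffeine alone first. After that, "The perception of bitterness is then tested in the presence of HED". Both ratings are to be compared between groups and visits, and the section does not say which is primary.

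Reference [7], the source of the 30%, is also cited in Section 2.1, where HED "can reduce the perception of the bitter taste of caffeine by approximately 40% [7" (the citation is to the same reference). Section C.1.1 says that bitterness may also fall somewhat in the control group through a placebo effect.

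**The concern.** A reader should be able to get from the inputs to the sample size. Here a difference three times its SD is paired with 16 patients per arm, far more than such an effect needs even at the 1% level. Either an input or the result is misreported.

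The inputs also do not visibly belong to the endpoint. They come from a source that the background cites for masking of caffeine's taste, whereas the trial compares changes over two weeks between groups. The spread of those changes determines the power, and the plan does not give it. At stake is how the result is read: a null finding cannot be weighed against a 90% figure that the design does not support.

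**Working it through.** **Inputs (Section B.1).** Difference 30%, SD 10%, significance level 1%, power 90%, dropout 20%, allocation 1:1. Standardised difference d = 30/10 = 3.0. Two-sided testing is assumed because the plan is silent; one-sided is also shown.

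**Attempt to reproduce 32.** For a two-sample t-test with n per arm, power = P(T > t(0.995; 2n−2)), where T is noncentral t with 2n−2 degrees of freedom and noncentrality d√(n/2).

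- n = 5: noncentrality 3√2.5 = 4.74, power 0.874.
- n = 6: noncentrality 3√3 = 5.20, power 0.956.

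So 6 evaluable per arm are needed. With dropout, 6/0.8 = 7.5, rounded up to 8 per arm, 16 in total (12/0.8 = 15 if the total is inflated instead).

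| Variant | Evaluable | Total with 20% dropout |
|---|---|---|
| Two-sample t, two-sided | 6 per arm | 16 (15) |
| Two-sample t, one-sided | 5 per arm | 14 (13) |
| Normal approximation, two-sided | 4 per arm | 10 |
| Normal approximation, one-sided | 3 per arm | 8 |
| Paired t as literally written, two-sided | 6 pairs | 8 |
| Paired t, one-sided | 5 pairs | 7 |
| Mann-Whitney, two-sided (simulated power about 92%) | 6 per arm | 16 |
| SD of change taken as 10√2 = 14.1, two-sided t | 9 per arm | 24 (23) |

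The range is 7 to 24. No variant reaches 32.

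**Power of 32 on the stated inputs.** After 20% loss, 16 × 0.8 = 12.8, taken as 13 per arm. At d = 3, power exceeds 99.99%. With an SD of 14.1 it is still 99.3%.

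**What 32 can detect.** Solving for 90% power at two-sided 1%:

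| Evaluable per arm | Detectable d | Largest SD for a 30-point difference |
|---|---|---|
| 12 | 1.71 | 30/1.71 = 17.6 |
| 13 | 1.63 | 30/1.63 = 18.4 |
| 16 | 1.44 | 20.8 (30 over the unrounded 1.445) |

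The upper row count of 16 is included because Section 4.1.2 counts as a withdrawal anyone who stops before Visit 3 at week 12, so some withdrawals will already have week 3 data.

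**Sensitivity to the missing SD.** The SDs below are assumptions; the documents give none for the change. The difference is 30 points on a 0–100 metric (3 units of the 0–10 rating), tested at two-sided 1%.

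| Assumed SD of change | Power, 13 per arm | Power, 16 per arm |
|---|---|---|
| 20 | 84% | 92% |
| 25 | 61% | 74% |
| 30 | 42% | 54% |

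**Placebo response.** Any improvement in the control arm reduces the difference. As an illustration only, an assumed 10-point improvement leaves 20 points, and with 13 per arm 90% power then needs an SD of at most 20/1.63 = 12.3.

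**The case against.** The strongest reply is that the discrepancy is conservative: on the plan's own inputs 32 patients are more than enough. That stands. A reader might infer that the trial is underpowered, but the documents do not show it. Power falls below 90% only if the SD of change exceeds about 18 to 21 points, and no document says whether it does.

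The 30% and the 40% need not conflict either. One source can report several figures, or the planners may have chosen a cautious one. Likewise, that the 30% is acute masking is a reasonable inference from Section 2.1, but what [7] measured cannot be seen here. What remains is that the plan does not say what the figure measures.

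A reader might also conclude that a total of 16 was mistaken for a group size of 16. The numbers coincide, but nothing in the documents shows this.

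Nor is the screening arithmetic wrong. 32/0.77 = 41.6, which fits the statement "Therefore, approximately 40 patients will need to be screened". Dividing 32 by the lower prevalence of 30% to obtain about 107 is not supported, because Section 4.1.1 brings patients to screening already suspected of bitter phantogeusia. Only the source of the input is unclear. Section B.1 uses 77% for a bitter disturbance after quoting 30–78% for bitter phantogeusia, while Section 2.1 says "Up to 77% of all female cancer patients suffer from chemotherapy-related taste disorder".

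Finally, stating a detectable difference for a fixed 32 works backwards and does not justify the number. That is fair, but it does tell the reader what the trial can show, which the present text does not.

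**Conclusion.** The statement in Section B.1 is wrong as written. Its inputs give about 16 patients (7 to 24 across the variants), and 32 patients on those inputs have power above 99.9%, not 90%. Actual power for the primary endpoint is unknown, because the plan gives neither the SD of the week 1 to week 3 change nor an allowance for a placebo response.

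The factor-of-two discrepancy rests on the printed inputs and a two-sided two-sample t-test. One-sided testing only lowers the required number. The sensitivity figures rest on assumed SDs and on 13 to 16 evaluable patients per arm at week 3. The plan's primary sample-size justification should be corrected, but nothing here shows that 32 is too few.

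**What to change.** Keep 32 and replace the 90% power sentence in Section B.1 with something like: *With 13 to 16 patients per arm evaluable at week 3, an independent-groups comparison of the change from week 1 to week 3 at a two-sided 1% level has 90% power for a standardised difference of about 1.63 (13 per arm) to 1.44 (16 per arm). For a between-group difference of 30 points this requires an SD of change of at most about 18 or 21 points respectively.* Add the sensitivity table, with its SDs labelled as assumptions, and say how a control-arm improvement is allowed for.

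State what the 30% (SD 10%) from [7] measures and reconcile it with the 40% in Section 2.1. State which caffeine rating is primary. Use pilot variability only if 500 ppm caffeine is rated there: Section 4.1.1 mentions various caffeine solutions without naming that concentration. Note also that the pilot enrols patients with any gynaecological malignancy, without requiring phantogeusia. Reconcile the 77% with the 30–78% range and with the any-taste-disorder figure in Section 2.1.

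The cost is a rewrite of Section B.1, with no change in recruitment. The downside is that the stated detectable effect becomes less favourable.

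### The 30% efficacy threshold equals the planned effect and is not reconciled with the t-test, so the plan has two success criteria and its 90% power can refer to only one of them

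*Combined protocol and SAP*

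**What the plan says.** Two parts of the Statistical Section use the same figure for different purposes.

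- **B.1, Sample Size** uses 30% as the planning effect: "An HED mouthwash leads to a 30% reduction in bitter perception (standard deviation 10%) [7], which describes the expected effect size". It continues: "Taking into account a 20% dropout rate, a 90% power level, and a significance level of 1%, this results in a sample size of 32". Allocation is 1:1 with 16 patients per group. The endpoint is a bitterness rating: "The patient rates bitterness perception on a continuous scale from 0 to 10".
- **B.3, Statistical Analysis** uses 30% as the threshold for efficacy: "The efficacy of the treatment is defined as a reduction in the perception of bitterness by more than 30% in the treatment group compared" with the placebo group. The next sentence reads: "The primary endpoint will be evaluated using a paired t-test". It gives no null value of 30%, no margin and no rule on a confidence limit.

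The primary endpoint in Section 3.3 and the efficacy evaluation in Section 4.1.5 refer only to bitterness from 500 ppm caffeine at weeks 1 and 3. Neither mentions a 30% threshold, and no other section links the threshold to the test.

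**The concern.** A threshold set at the planning value behaves differently from a test of no difference. If the mouthwash works exactly as assumed, the t-test should usually be significant, but the observed reduction will fall on either side of 30% with equal probability. The power statement in B.1 therefore says nothing about the chance of meeting the definition in B.3.

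The stake is the primary conclusion. Suppose the observed reduction versus placebo is 25% with p below 0.01. The t-test makes this a positive trial, while the definition of efficacy makes it a negative one. Since the plan does not say which criterion governs, the choice could be made after the result is known.

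**Working it through.** **Inputs.** From B.1: expected reduction 30%, SD 10%, power 90%, significance level 1% (sidedness not stated), dropout 20%, 16 per arm. From B.3: threshold above 30% versus placebo. After dropout, 16 × 0.8 = 12.8, so about 13 evaluable per arm. Assumptions made here: SD 10% means 10 percentage points and is the between-patient SD within each arm, the test is two-sided unless noted, and the estimate is approximately normal.

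**1. The plan's own sample size.** Normal approximation: n per arm = 2 × (2.576 + 1.282)² × (10/30)² = 3.3, so 4 per arm, and 8/0.8 = 10 in total. The exact two-sample t gives 6 per arm (12/0.8 = 15). The paired t gives 6 pairs (6/0.8 = 7.5, so 8). An SD multiplied by √2 for a change score gives 7 per arm by the normal approximation (14/0.8 = 17.5, so 18). One-sided versions are smaller. None reaches 32. For 90% power with 13 to 16 per arm, the SD would have to be about 18 to 21 points, so an SD of 20 is also shown below. The present point does not depend on this mismatch.

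**2. Chance that the point estimate exceeds 30%.** With SE = SD × √(2/n),

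P(estimate > 30) = 1 − Φ((30 − true)/SE).

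At a true net reduction of 30 the numerator is zero, so P = 1 − Φ(0) = 50%, whatever the SD or n. Simulation (200,000 trials per setting) gave 49.9% to 50.1%. Defining the reduction as a ratio of arm means (assumed placebo mean 6, SD 1 or 2, 13 per arm) also gave 50%.

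**3. Other true effects.** These figures, unlike the 50%, depend on the SD and n. For example, at SD 10 and 13 per arm, SE = 10 × √(2/13) = 3.92, and a true 25 gives 1 − Φ(5/3.92) = 10%.

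| True net reduction | SD 10, n 13 (SE 3.92) | SD 10, n 16 (SE 3.54) | SD 20, n 13 (SE 7.84) | SD 20, n 16 (SE 7.07) |
|---|---|---|---|---|
| 25% | 10% | 8% | 26% | 24% |
| 30% | 50% | 50% | 50% | 50% |
| 35% | 90% | 92% | 74% | 76% |
| 40% | 99.5% | 99.8% | 90% | 92% |

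**4. The two criteria compared at a true 30%.** At SD 10 and 13 per arm, power of the two-sample t-test against zero is above 99.9%. At SD 20 it is 84% (13 per arm) or 92% (16 per arm). Requiring both p < 0.01 and an estimate above 30% gives about 50% at SD 10 or 20. At an assumed SD of 30 it gives 39% (13 per arm) or 46% (16 per arm).

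**The case against.** The strongest reply is that B.1 attaches its 90% to the t-test and never promises a 90% chance of exceeding 30%. On that view the power statement is not false, and the 30% sentence is a benchmark of relevance that leaves the primary test untouched. Requiring significance plus a relevant estimate is also a legitimate design, and a 50% chance at the threshold is its normal property. The first part stands: a reader might infer that the plan misstates its power for the 30% criterion, but the plan makes no such claim. What remains is that B.3 presents the 30% as the definition of efficacy, without calling it a benchmark or saying how it combines with the test.

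A second reply is that 30% might be a patient-level cut-off, because B.3 also plans a logistic regression on response and defines no responder. The wording compares the treatment group with the placebo group, which favours a group-level reading, but the text does not settle it.

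A third reply is that the true effect may be larger. Section 2.1 gives about 40% from the same source (reference 7), which would raise the chance well above 50%. This is fair, but B.1 plans on 30%. There is also a pull the other way: B.1 does not say its 30% is net of placebo, and Section C 1.1 allows for a placebo response, which could bring the net effect below 30%.

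**Conclusion.** The point holds in conditional form. B.3's threshold equals B.1's planning effect, its role is undefined, and the 90% power can apply only to the t-test. If the threshold is a success rule on the point estimate and the true net reduction is 30%, the chance of meeting it is about 50% at any sample size. Away from a true 30% the chance moves in both directions. The figures of 10% at a true 25% and 90% at a true 35% assume an SD of 10 percentage points and 13 evaluable patients per arm. At an SD of 20 they become 26% and 74%.

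Three stronger readings are not supported:

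- A reader might infer that the trial can never have more than a 50% chance of meeting its definition. That fails if the true net effect exceeds 30%.
- A reader might infer that the trial would be declared ineffective half the time even if the mouthwash works as planned. That is a consequence of one reading of B.3, not a documented decision rule.
- A reader might infer that a lower confidence limit has to exceed 30%. No section contains such a rule.

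**What to change.** Change the efficacy sentence in B.3. Define success by the primary between-arm test of the week 1 to week 3 comparison at the stated 1% level. Report the relative reduction versus placebo with its confidence interval, and describe 30% as a benchmark of relevance that does not decide success.

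If the sponsor prefers to keep 30% as a hurdle, B.3 should say which quantity must exceed it (point estimate, confidence limit or individual response) and whether significance is also required. B.1 should then restate the power for that criterion under an assumed effect larger than 30%.

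The first option costs one sentence and should be made before unblinding. Its downside is that a significant effect below 30% would count as positive and would have to be interpreted for relevance. The second option requires a new sample-size calculation and may change the number of patients.
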